4.11 Missing data

The Valencia Region databases have a very low percentage (0.02%) of unregistered data; subjects with missing information will be excluded for the study.

Patients with incomplete follow-up will account for the analysis as of the date of loss of follow up.

4.12 Data management

The process for data obtaining in The Valencia Region will have the next steps:1) Ethics Revision Board (ERB) approval; 2) General Director of Public Health approval for data transfer; 3) Telematic data request; 4) PROSIGA committee approval of data requested; 5) Data extraction; 6) Data checking and cleaning; 7) Potential new extraction (if errors); 8) Data analysis.

All data files will be received in plain text (.txt) format with the variables separated by pipes. Identification data will be dissociated with the same seed. The information from the different sources will be merged by the subject identification number (SIP number). All files will be passed a check list to guarantee the quality of the data and detect possible errors in the extraction.

Population will be determined by the SIP file; only data from SIA, CMBD and RedMIVA that intersect with the population will be considered. Data in long format (two or more records by subject) will be transformed in wide format having a subject in each record.

Txt files will be transformed into analytical datasets suitable for further sharing and analysis. The analytical dataset will contain anonymized data only. The data transformation files will be programmed in R.

5. Regulatory and Ethical considerations

The study will be conducted in accordance with all applicable regulatory requirements, including all applicable subject privacy requirements, the Declaration of Helsinki, and the International Ethical Guidelines for Epidemiological Investigations.

The study will be submitted for approval to the institutional review board.

For transparency purposes, the protocol will be posted into the European Network of Centres for pharmacoepidemiology and pharmacovigilance (ENCePP) website.

1. BUDGET

roject phase	Budget	Project: Impact of COVID-19 pandemic on HZ risk: A population- based study using Real World Data			
	Task	Sub-task	Total cost		
	Pre-work				
	Bran agai	Previous meetings and emails	-		
	Proposal	Proposal's coordination			
		Brain storming's meeting			
		Literature review			
		Proposal's writing Statistica analysis			
		Budget	-		
	Contract				
		Head of Fisabio's approval management Signature's management	-		
		Fisabio's bureaucracy management	-		
	Study coordinator				
		Responsible for meeting the project scope, time and cost requirements			
		Monitor and periodically review the status of the project Gantt chart			
Phase I		Meeting plan	22250		
	Protocol				
		Design			
		Literature review Writing	-		
		Writing support	-		
		Statistical analysis			
		Follow-up meetings with GSK			
	Statistical Analysis Plan	Thinking, preparation and writing	-		
		Follow-up meetings with GSK			
	Ethical requirements				
		AEMPs			
		ERB bureaucracy Clarifications			
		Amendments			
		Taxes			
	Electronic databases (5 registries)	De sus et es etter			
		Request creation Data providers contacts	-		
		Bureaucracy			
		Script			
		Data extraction			
		Data quality checking Corrections			
		New extraction after corrections	-		
Phase II		Follow up	43170		
i nase n	Data analysis	Date cleaning tobulation and fusion			
		Data cleaning, tabulation and fusion Mathematical model creation	4		
		Data analysis, adjustments	-		
		Results interpretation and discussion			
		Preliminary report			
		Final Report Web App (Shiny) for the preentation of the results	1		
	Folow-up		1		
		Follow-up meetings with GSK	1		
	Comunications				
Phase III		International/national meeting Scientific paper writing	3080		
i nase in		Submission 1/2 journalts			
			1		
			68500		
		Budget for 2021			
		Budget for 2022			
		Indirect costs (15%)			
		Total cost	78775		

2. TIMELINES

Tasks/Time (months)	ene-21	feb-21	mar-21	abr-21	may-21	iun-21	iul-21	ago-21	sept-21	oct-21	nov-21	dic-21	ene-22	feb-22	mar-22	abr-22	may-22	jun-22	iul-22	ago-22	sept-22
Proposal	***	100-21	1101-2-1	001-21	may-21	jun-2 i	jui-2 i	ugo-2 i	Sopt-21	001-21	1104-21	010-21	0110-22	100-22	11101-22	001-22	may-22	Junezz	101-22	ugo-zz	JOPTEL
Study design and protocol		••																			
and SAP																					
IBR approval			•																		
Contract signature				•																	
Data delivery approval				•																	
Data extraction and collection (5 registries)							•			•			•								
Data cleaning and tabulation																					
Data management and analysis																					
Results interpretation and discusion														•	•						
Primary Objective																•					
Secondary Objectives																	•				
Provisional Report/Review and discusion																			••		
Final Report																				••	
Manuscript Preparation and Submission																					
* Follow Up Meetings																					

3. ANNEX 1

3.1. LIST OF VARIABLES TO BE EXTRACTED FROM DATABASES

Data privacy will be protected by using anonymised data (see 2.2. section). The following variables will be requested to the different databases for the period from 1 January 2007 to 31 January 2015 for subjects \geq 18 years old:

Data to be extracted from SIP:

- Identification block including SIP number, sex, date of birth and other geographical of birth, place and date of registration (excluding identifying data as surnames, ID card number, phone numbers, etc.)
- Assignation block (including municipality, healthcare district, etc)
- Regular location block that includes complete address, health map information as health department and census information among others (excluding exact data that allows the exact residence location of the subjects)
- Cessation block including cessation cause and description, cessation date and date of death (when applicable)
- APSI code
- Barthel Index

Data to be extracted from SIA

- SIP number

Morbidity database

- Date of diagnosis activation (diagnosis of interest)
- Date of diagnosis deactivation (diagnosis of interest)
- Diagnosis description (diagnosis of interest)
- ICD-codes (diagnosis of interest)

Outpatient visits database

- Date of the visit
- Diagnosis description
- ICD-code

Specialist visits database

- Date of the visit
- Diagnosis description
- ICD-code
- Professional attendance (GP/Specialist)
- Specialist service

For any diagnosed code related to HZ (see section 4.3) and comorbidities (see section 4.6.3)

Data to be extracted from MBDS:

- Anonymized Personal Identification Number (SIP)
- Birth date
- Sex
- Municipality of residence
- Postal code
- Health department
- Health care district
- Date of hospital admission
- Date of hospital discharge
- Diagnoses at discharge (main and secondary diagnoses)
- Procedures during the hospitalization
- Discharge destination (destination on discharge)
- ICU (any position)
- POA

For any diagnosed code related to HZ (see section 4.3) and comorbidities (see section 4.6.3) and SARS-Cov-2 (J12.89, J20.8, J40, J22, J98.8, J80, R65.20, R65.21, R05, R06.02, R50.9, R43.0, Z20.828, Z03.818, Z11.59 O98.5, B97.29 or U07.1 and B34.2)

Data to be extracted from RedMIVA

- SIP number
- Date of laboratory test (dd/mm/yyyy)
- Date of test result
- Sample type
- Laboratory test (PCR, antigen, etc)
- Result

For any SARS-Cov-2 test

Source	Dataset	Variable	Label	Туре	Coding
SIP	Identification block	SIP	SIP number	character	Random key

SIP	Identification block	sex	Sex	character	Sex_fmt
SIP	Identification block	birth_date	Date of birth	date	yyyy-mm-dd
SIP	Identification block	birth_place	Geographical birth	date	yyyy-mm-dd
SIP	Identification block	nationality	nationality	character	Natio_fmt
SIP	Identification block	reg_status	Registration status	character	Reg_fmt
SIP	Regulation block	reg_date	Date of registration	date	yyyy-mm-dd
SIP	Regulation block	PC	Postal code	integer	Pc_fmt
SIP	Regulation block	muni	Municipality	Character	Muni_fmt
SIP	Regulation block	province	Province	Character	Prov_fmt
SIP	Assignation block	hc_district	Health care district	Character	Hc_dist_fmt
	Assignation block	h_department	Health department	Character	H_dep_fmt
SIP		APSI	APSI code	Character	
SIP	Cessation block	ces_date	Cessation date	Date	yyyy-mm-dd
SIP	Cessation block	death_date	Date of death	Date	yyyy-mm-dd
MBDS		SIP	SIP number	Character	
MBDS		hosp	Hospital	Character	
MBDS		h_department	Health department	Character	
MBDS		admission_date	Date of hospital admission	Date	yyyy-mm-dd
MBDS		dlscharge_date	Date of hospital discharge	Date	yyyy-mm-dd
MBDS		d_i (i= 1,,30)	Diagnoses at discharge (any position)	character	ICD-9 ICD-10
MBDS		p_i (i= 1,, 30)	Procedures during the hospitalization	character	ICD-9 ICD-10
MBDS		Des_discharge	Discharge destination (destination on discharge)	Date	yyyy-mm-dd
MBDS		Death_cause	Cause of death	character	Two diagnoses ICD coded
MBDS		ICU	ICU (any position)	integer	Days
SIA-GAIA	1	SIP	SIP number	character	Random key

SIA	Morbidity database	Act_date	Date of diagnosis activation (diagnosis of interest)	date	yyyy-mm-dd
SIA	Morbidity database	Dea_date	Date of diagnosis deactivation (diagnosis of interest)	date	yyyy-mm-dd
SIA	Morbidity database	Dx_desc	Diagnosis description (diagnosis of interest)	character	
SIA	Morbidity database	Dx_code	ICD-code (diagnosis of interest)	character	ICD-9 ICD-10
SIA	Outpatient visits database	Visit_date	Date of the visit	date	yyyy-mm-dd
SIA	Outpatient visits database	Dx_desc	Diagnosis description	character	
SIA	Outpatient visits database	Dx_code	ICD-code	character	ICD-9 ICD-10
SIA	Specialist visits database	Visit_date	Date of the visit	date	yyyy-mm-dd
SIA	Specialist visits database	Dx_desc	Diagnosis description	character	
SIA	Specialist visits database	Dx_code	ICD-code	character	ICD-9 ICD-10
SIA	Specialist visits database	Specialist	Professional attendance (GP/Specialist)	character	Profess_fmt
SIA	Specialist visits database	Service	Specialties Service	character	Service_fmt
RedMIVA		SIP	SIP number	character	Random key
RedMIVA		Lab_date	Date of laboratory test	date	yyyy-mm-dd
RedMIVA		micro	Microorganism/antigen	character	
RedMIVA		Res_date	Date of test result	date	yyyy-mm-dd
RedMIVA		Sample_type	Sample type	character	
RedMIVA		Lab_test	Laboratory test	character	

RedMIVA	result	Result	character	Res_fmt
RedMIVA	Antimicro_res	Antimicrobial resistance	character	
SIV	SIP	SIP number	character	Random key
SIV	Vaccine_type	Vaccine type (PCV7, PCV10, PCV13 or PPV23)	character	
SIV	Dose	Dose	integer	
SIV	Admin_date	Administration date (anti- pneumococcal vaccination)	date	yyyy-mm-dd

Format	Categories				
Sex_fmt	Female				
Sex_fmt	Male				
Natio_fmt	Spanish, Other				
reg_fmt	unregistered				
reg_fmt	unregistered <1 more	nth			
reg_fmt	unregistered $\geq 1 \text{ mod}$	nth			
reg_fmt	registered				
Muni_fmt	542 municipalities				
PC_fmt	Ex: 46112				
Prov_fmt	Alicante				
Prov_fmt	Castellón				
Prov_fmt	Valencia				
Hc_dist_fmt	241 health care dist				
H_dep_fmt	24 health department				
	00	NO ASIGNADO			
	01	DP1 VINAROS			
	02	DP2 CASTELLON			
	03	DP3 LA PLANA			

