4.2 Study population and period

The cohort will include all subjects older than 18 years living in Valencia Region, registered in the Regional Health System (RHS) (over 98%) from January 1st 2018 to, at least, December 31st 2020 (or date of data extraction). The inclusion and exclusion criteria will be the following:

Inclusion criteria: Subjects aged 18 years and above covered by the RHS and residing in the Valencia Region during study period.

Exclusion criteria:

- Subjects with less than 12 months of registration to the RHS and subjects with incorrect codification.
- Subjects vaccinated against HZ before the diagnosis of SARS-CoV-2
- Subjects vaccinated against SARS-CoV-2 before the diagnosis of SARS-CoV-2

Start of follow-up: The start of the follow-up is defined as the latest of start of the study (1st January 2018), first date of registration in the database or date of the 18th birthday.

End of follow-up: The end of the follow-up is defined as the earliest of the following cases:

- End of study period
- Loss of follow-up (exit of RHS)
- Exitus
- Vaccination with HZ vaccine
- Vaccination with COVID-19 vaccine
- Development of HZ

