4.6.3 Comorbidities

Comorbidities that have been identified as risk indicators for HZ will be considered for the analysis. These conditions will be identified by systematic search of ICD-codes in the hospital or ambulatory databases, MBDS or SIA. Subjects will be considered to

Disease classification	ICD-10
Diabetes	E10-E14
COPD	J44
Ischemic heart disease	120-125
Other heart disease	127-152
Kidney disease	N18-N19
Immunocompromised	
HIV	B20-B24
Cancer	C00-D49
TOTS	Z94
IBD	K50-K51
RA	M05-M14
SLE	M32

have a given condition from the first appearance of the comorbidity-related diagnosis date until the end of the follow-up period.

COPD: chronic obstructive pulmonary disease, HIV: human immunodeficiency virus, TOTS: Transplanted organ and tissue status, IBD: inflammatory bowel disease, RA: rheumatoid arthritis, SLE: systemic lupus erythematous.

Presence of any comorbidity.

This is a binary variable indicating whether the patient has at least one comorbidity defined above.

Number of underlying conditions

This is a categorical variable indicating the number of comorbidities (0, 1, 2, 3+).

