4.8 Data collection

The following variables (Annex 1) will be requested to the different databases for the period from July 2017 until at least December 31st 2020 (depending on the date of data extraction) for subject's \geq 18 years. Data privacy will be protected by using dissociated data.

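### Annex 1 requests only pneumococcal vaccine data, so the HZ- and COVID-19-vaccine rules in 4.2 cannot be applied as specified; its extraction window contradicts 4.8, and the 4.8 window gives uneven comorbidity history for secondary objective 2

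*Protocol*

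**What the plan says.** - **Vaccine rules.** Section 4.2 excludes people vaccinated against HZ, or against SARS-CoV-2, before their SARS-CoV-2 diagnosis. It also ends follow-up at either vaccination; one of the listed end points is "Vaccination with COVID-19 vaccine". Section 4.6 names SARS-CoV-2 vaccination among the covariate information and points to Annex 1 for the variables.
- **Data request.** Section 4.8 says the Annex 1 variables will be requested "for the period from July 2017 until at least December 31st 2020". Annex 1 itself (3.1) says they will be "requested to the different databases for the period from 1 January 2007 to 31 January 2015".
- **Vaccine fields.** The SIV rows of the Annex 1 table are a person identifier, "Vaccine type (PCV7, PCV10, PCV13 or PPV23", a dose, and "Administration date (anti- pneumococcal vaccination". The narrative list before that table has no vaccine block.
- **Registries.** Section 4.7 describes SIP, SIA, MBDS and RedMIVA as the registries to be used. Section 4.12 adds that, for the population defined by SIP, "only data from SIA, CMBD and RedMIVA that intersect with the population will be considered". The budget and the timeline both count five registries.
- **Comorbidity rule.** Under 4.6.3 a person is taken to "have a given condition from the first appearance of the comorbidity-related diagnosis date until the end of the follow-up period". The codes listed there are ICD-10 only.

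**The concern.** Four rules in 4.2, two exclusions and two censoring rules, decide who is eligible and when person-time stops, including for the primary objective. They need HZ and COVID-19 vaccination dates, and the data request names neither vaccine. If the request is filled as written, vaccinated person-time stays in both comparison groups.

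The two extraction windows are a second, separate defect. A data provider working from Annex 1 and one working from 4.8 would return different years.

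The third issue arises even if 4.8 governs. A comorbidity counts from its first recorded diagnosis, and the records open only six months before the study. Recorded comorbidity can therefore rise with calendar time because of the length of history alone. Secondary objective 2 adjusts for comorbidity when comparing the pandemic with the pre-pandemic period. People labelled as having no comorbidity would then include more undetected comorbidity, and so a higher HZ rate, before the pandemic than during it. That pushes the adjusted ratio below its true value.

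**Working it through.** The protocol states no figure on this point to reproduce. The first two steps compare sections and dates; the third is a sensitivity calculation.

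**1. Vaccine fields against vaccine rules.** 4.2 needs HZ-vaccine and COVID-19-vaccine dates. Annex 1 contains no field for either. This holds whichever window governs.

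**2. Dates** (July 2017 taken as 1 July).
- End of Annex 1 window, 31 January 2015, to opening of the 4.8 window: 882 days.
- 31 January 2015 to study start, 1 January 2018: 1,066 days.
- 31 January 2015 to pandemic start, 14 March 2020: 1,869 days.
- 1 July 2017 to 1 January 2018: 184 days of history.
- 1 July 2017 to 14 March 2020: 987 days of history.
- 1 July 2017 to 31 December 2020: 1,279 days of history.

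The windows do not overlap. Under 4.8, available history grows 5.4-fold between study start and pandemic start (987/184), but only 1.3-fold within the 2020 part of the pandemic period (1,279/987).

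**3. Possible bias in secondary objective 2.** Assumed, because the protocol gives no values: true comorbidity prevalence *p* of 30% or 50%; HZ rate ratio for comorbidity *R* of 1.3 or 1.5; sensitivity of recorded comorbidity *s* of 60% or 80% pre-pandemic, rising to 85% or 95% in the pandemic. From the protocol's dates, assuming follow-up ends on 31 December 2020: 803 pre-pandemic and 293 pandemic days. There is no true period effect.

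Labelled-comorbid share = *ps*. Relative HZ rate in those labelled free of comorbidity = [*p*(1 − *s*)*R* + (1 − *p*)] / (1 − *ps*). The Mantel-Haenszel ratio weights each stratum by *t*₀*t*₁/(*t*₀ + *t*₁), where *t* is share × days.

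Largest bias (*p* = 0.5, *R* = 1.5, *s* from 0.60 to 0.95):
- Labelled share: 0.300, then 0.475.
- Relative rate in those labelled free: 0.800/0.700 = 1.143, then 0.5375/0.525 = 1.024.
- Weights: comorbid 240.9 × 139.2/380.1 = 88.2; free 562.1 × 153.8/715.9 = 120.8.
- Ratio: (1.5 × 88.2 + 1.024 × 120.8) / (1.5 × 88.2 + 1.143 × 120.8) = **0.947**.

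Smallest bias (*p* = 0.3, *R* = 1.3, *s* from 0.80 to 0.85):
- Labelled share: 0.240, then 0.255.
- Relative rate in those labelled free: 0.778/0.760 = 1.0237, then 0.7585/0.745 = 1.0181.
- Ratio: **0.996**.

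The other 14 combinations lie between these. At 80% rising to 85%, all four results are 0.992 to 0.996.

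**Standard error for scale.** With 4 million adults (4.9.1) and 5.02 per 1,000 person-years (4.9.2):
- Pre-pandemic: 4,000,000 × 803/365.25 × 0.00502 ≈ 44,146 cases.
- Pandemic: 4,000,000 × 293/365.25 × 0.00502 ≈ 16,108 cases.
- SE(log RR) = √(1/44,146 + 1/16,108) = **0.0092**.

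**The case against.** The strongest reply is that these are stale entries and the intention is clear. Section 4.8 requests study-period data. Annex 1 itself asks for any SARS-CoV-2 test, which cannot fit a 2015 cut-off. A vaccination registry is named in 4.7.1 as part of VID, and the count of five registries against four described suggests that a fifth is planned. Much of this stands, and it rules out several stronger readings.

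- A reader might infer that no study-period data would be collected. The protocol does not support that: 4.8 asks for them, so this is a contradiction to reconcile.
- A reader might infer that the wrong window is what disables the vaccine rules. It is not; the list of vaccine products does that.
- A reader might infer that the vaccine register was forgotten. It has rows in Annex 1. The fault is that those rows name other vaccines and that 4.7 and 4.12 do not describe it.
- A reader might infer that comorbidity history is six months throughout, or that the primary result is biased by it. Six months applies only at 1 January 2018. The primary comparison lies within the pandemic, where both groups draw on at least 987 days of database history.

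Two further points for the other side hold. The SIA morbidity table requests diagnosis activation dates, so chronic diagnoses opened before July 2017 may be returned; the protocol does not say whether they would be. Six months also matches the HZ-free interval in 4.3, so the short history does not harm the incident-case definition.

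The missing ICD-9 comorbidity codes are a weak point on their own. MBDS changes to ICD-10 after 2016, and the Annex coding column reads the same for MBDS and SIA. The codes are needed mainly if older diagnoses are requested.

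Clear intent does not answer the vaccine point: no section names HZ or COVID-19 vaccine fields to be extracted.

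**Conclusion.** The point stands in three parts of unequal weight.

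1. **Vaccine fields: must be corrected.** The two exclusions and two censoring rules cannot be applied from the data specified. The effect is small if follow-up ends on 31 December 2020. It matters if follow-up runs to data extraction, which 4.2 allows and the timeline places in 2021 and January 2022: post-vaccination time would then be kept against the protocol's own rule. The documents do not allow that effect to be sized.
2. **Extraction window: must be reconciled.** Annex 1 and 4.8 contradict each other, and the Annex window lies wholly before the study.
3. **Comorbidity history: a lesser point, for secondary objective 2.** The adjusted ratio can be biased downward, from 0.4% (less than half a standard error) to 5.3% (nearly six standard errors). This rests entirely on the assumed prevalence, rate ratio and sensitivities, and on activation dates not recovering older diagnoses.

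**What to change.** (a) In Annex 1, replace the pneumococcal SIV fields with HZ and COVID-19 vaccine type, dose and administration date. Request HZ vaccination from the start of available records, because that exclusion has no start date and a pull from July 2017 would miss people vaccinated before then. Add SIV to 4.7 and to the merge rule in 4.12.

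(b) Replace the Annex 1 window with that of 4.8, and state one fixed end date in both places.

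(c) Request comorbidity diagnoses from 2007, since the protocol calls SIA reliable from then, and keep the first-appearance rule. History would then be 11 years at study start and about 13.2 years at pandemic start, a far smaller relative change than 184 to 987 days. Add ICD-9 equivalents to 4.6.3 for the earlier years.

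The cost is a corrected data request and a longer diagnosis pull from registries already in use. It is cheapest before extraction; afterwards it means a repeat request and extraction through the steps in 4.12.

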	04 DP4 SAGUNTO				
	05 DP5 VALENCIA CLINICO				
	06 DP6 VALENCIA ARNAU DE VILANOVA				
	07	DP7 VALENCIA LA FE			
	08	DP8 REQUENA			
	09	DP9 CE JUAN LLORENS TORRENT			
	10	DP10 VALENCIA DR PESET			
	11	DP11 LA RIBERA			
	12	DP12 GANDIA			
	13	DP13 DENIA			
	14	DP14 DENIA			
	15	DP15 ALCOI			
	16	DP16 VILA JOIOSA			
	17	DP17 ALICANTE SAN JUAN			
	18	DP18 ELDA			
	19	DP19 ALICANTE			
	20	DP20 ELX			
	21	DP21 ORIHUELA			
	22	DP22 TORREVIEJA			
	23	DP23 MANISES			
	24	DP24 ELX CREVILLENT			
APSI_fmt	Ex: 1SH2004112	51610110ваз			

	allows the APSIG co requested	e segmenta odes vary l for each s	ation of t over time subject.	o of a set of dimensions, each representing the entire integrated population in SIP. e, 3 codes at the beginning, middle and end tructured according to the following table:		
	Desde	Hasta	Long.	Descripción	Valores	
	1	1	1	Situación de empadronamiento	1,2,3	
	2	2	1	Indicador de nacionalidad española	S,N,D	
	3	3	1	Sexo	H,M	
	4	11	8	Fecha de nacimiento	yyyymmdd	
	12	13	2	Departamento de asignación	1,2,3, 24	
	14	15	2	D1. (Financiación cobertura)	10,20,30,40,51,52,60	
	16	16	1	D2. (Situación de residencia)	0,1,2,3,4	
	17	18	2	D3. (Migraciones)	10, 21,22,23,31,32,33,4	
	19	19	1	D4. (Relación con la actividad laboral)	A,B,C,D,E,O	
	20	21	2	D5. Grupos y subgrupos de Aseguramiento	A1,A2,A3,B1,B2,B3,B4,C	
	22	25	4	D6. Conjuntos geopolíticos	Pos 22 – 0,1,2,3,4,5,6,7, Pos 23 a 25 – según tab	
	26	26	1	D7. Perfil de Vulnerabilidad APSI	0,1,2,3,4,5	
	27	32	6	D8. Unidad de residencia	Pos 27–28 1 a 15 Pos 29–30 0,1,2,3,4,5 Pos 31–32 00	
	33	34	2	D9. RAF-Renta(régimen de aportación Farmacia y Niveles de Renta)	Pos 33-34	
	35	36	2	Zona de asignación	ZZ la zona asociada a Departamento de asigna 00, 01,18 dependi departamento corresp	
Profess_fmt	Pneumologist,,					
Service_fmt	Endocrinology ,,etc.					
Res_fmt	Positive					
Res_fmt	Negative					
Res_fmt	Other					

Signed

[name] [name] (principal investigator)
